STUDY PROTOCOL

**The Pathophysiology of Swallowing Impairment in
People recovering from COVID-19 Infection**

NCT 04537650

PI: [name].

Swallowing Rehabilitation Research Laboratory

KITE Research Institute, Toronto Rehabilitation Institute, University Health Network

TABLE OF CONTENTS

LIST OF ABBREVIATIONS	3
PROTOCOL SUMMARY	4
1.0 General Information	6
2.0 Introduction	7
3.0 Study Objectives and Hypothesis.....	7
3. 1 Purpose	7
3.2 Objectives.....	9
3.3 Hypothesis.....	10
4.0 Study Design.....	10
Data Collection Procedure	10
Compensation	14
File Transfer	14
ClinicalTrials.gov Registration	14
5.0 Selection of Subjects	14
Participants	14
Recruitment	14
Inclusion Criteria	15
Exclusion Criteria.....	15
6.0 Risks and Benefits	15
Risks	15
Benefits	16
Incidental Findings	16
7.0 Statistics	16
8.0 Data Safety and Monitoring Plan.....	17
9.0 Data Handling and Record Keeping	17
10.0 Conflicts of interest.....	18
11.0 Additional Ethics Reviews	18
12.0 References	18

LIST OF ABBREVIATIONS

PrC-19	People recovering from COVID-19
VFSS	Videofluoroscopic Swallowing Study
LVC	Laryngeal Vestibule Closure

PROTOCOL SUMMARY

Full Title	The Pathophysiology of Swallowing Impairment in People Recovering from COVID-19 Infection.
Short Title	Swallowing impairment after COVID-19.
Sample Size	N=100 (approximately 25 at each collaborating site and 50 at the University Health Network)
Study Population	Patients who are recovering from COVID-19 infection.
Accrual Period	October 15, 2020 to January 31, 2022
Study Design	This is an observational study, in which people recovering from COVID-19 infection will attend two outpatient clinic visits for a comprehensive swallowing assessment. The assessment will include a videofluoroscopy, measurement of respiratory-swallow coordination using a digital stethoscope, measures of tongue and cough strength and patient reported measures that will help us to understand the presence and impact of swallowing impairment (dysphagia) in this population.
Study Duration	October 15, 2020 to January 31, 2022
Procedure	Participants will be asked to attend two 60 minute visits where we will capture a videofluoroscopy, measurement of respiratory-swallow coordination using a digital stethoscope, measures of tongue and cough strength and patient reported measures that will help us to understand the presence and impact of swallowing impairment (dysphagia) in this population. If requested, it may be possible to arrange for both visits to take place on the same day.
Primary Outcomes	
 • Frequency of boluses (per consistency) on which the participant displays unsafe swallows, defined as scores of 3 or higher on the Penetration-Aspiration Scale (Rosenbek et al., 1996). • Frequency of boluses (per consistency) on which the participant displays inefficient swallows, defined as swallows with pharyngeal residue measured to fill 1% or more of an anatomical reference scalar $[(C2-4)^2]$ on a lateral view x-ray.
Secondary Outcomes	
 • Frequency of boluses (per consistency) on which the participant displays time-to-laryngeal-vestibule-closure more than 1 standard deviation above the healthy reference mean ([name] et al., 2019). • Frequency of boluses (per consistency) on which the participant displays laryngeal-vestibule-closure duration more than 1 standard deviation below the healthy reference mean ([name] et al., 2019). • Pixel-based measurement of pharyngeal area at rest from a single a lateral view x-ray image, and classified as below or above 1

	
standard deviation from the healthy reference mean ([name] et al., 2019).
 
 • Frequency of boluses (per consistency) on which the participant displays pharyngeal area above the 75th percentile healthy reference value on the frame of maximum constriction ([name] et al., 2019). • Frequency of boluses (per consistency) on which the participant displays multiple swallows, above the 75th percentile healthy reference value ([name] et al., 2019).
Exploratory Outcomes	
 • Frequency of boluses (per consistency) on which post-swallow inspiration is seen immediately following the swallow. • Maximum value across 3 repetitions of a maximum tongue-palate press task, measured using the Iowa Oral Performance Instrument in an anterior position. • Range of diet textures included in the participant's diet, measured using the International Dysphagia Diet Standardisation Initiative Functional Diet Scale. • Total and individual question scores on the Sydney Swallow Questionnaire. • Reported dyspnea using the Modified Medical Research Council Dyspnea Scale. • Maximum peak voluntary cough flow across 3 repeated coughs through a peak-flow meter. • Patient report of any changes (Yes/No) they have experienced in taste or smell associated with their COVID-19 infection.
Endpoints of the study	
Recruitment and completed data collection in 100 patients across the 3 study sites.

2.0 Introduction

The recent spread of COVID-19 has led to an international pandemic, with >90 million confirmed cases to date worldwide, of which 22.5 million confirmed cases and >375,000 deaths have been reported in the USA. Infected individuals commonly experience severe respiratory difficulties and pneumonia, leading to hospital admission and the need for intensive care and mechanical ventilation. Emerging evidence suggests that impaired taste and smell may be early markers of the disease, and that in severe cases, there may be neurological damage in the medulla, an important brainstem control site for both respiration and swallowing (Jean, 2001). Given the overlapping neuroanatomical regulation of breathing and swallowing, we hypothesize that dysphagia (swallowing impairment) will be common in People recovering from COVID-19 (PrC-19) and associated with poorer outcomes. Dysphagia involves impairments of swallowing safety and/or efficiency (Lovato and deFilippis, 2020). Impaired swallowing safety involves penetration or aspiration of material into the airway; impaired swallowing efficiency involves pharyngeal residue after the swallow, which, in turn, becomes a risk for secondary aspiration ([name] et al., 2020). Aspiration is considered a risk for pneumonia (Pikus et al., 2003; Arnold et al., 2016; Martino et al, 2005), which is a frequent reason for readmission to hospital (Prescott et al., 2015).

We will establish 3 regional research clinics that will offer comprehensive swallowing assessments to PrC-19 after initial recovery and a confirmed negative test for continuing COVID-19 infection. These research clinics will draw on established connections to clinicians in the Toronto area (PI [name]); the Hamilton-Niagara region to the west of Toronto (Co-I [name]) and in Gainesville, Florida (Co-I [name]). The assessments will include the collection of case history information, videofluoroscopy (i.e., a dynamic swallowing x-ray), use of a novel digital stethoscope to measure respiratory-swallow coordination, measures of other risk factors for dysphagia (e.g. bulbar muscle strength) and patient-reported outcomes. Detailed analyses of the videofluoroscopy swallowing studies (i.e. dynamic x-rays) will identify specific measures of swallowing that fall outside the range of normal variation based on comparison to healthy reference values established through our research program exploring swallowing physiology on liquids of different consistencies.

3.0 Study Objectives and Hypothesis

3.1 Purpose

The proposed studies will be an extension of our current work exploring swallowing physiology in healthy adults and patients with dysphagia of various etiologies (Amyotrophic Lateral Sclerosis, traumatic Spinal Cord Injury, oropharyngeal cancer treated with radiation, Chronic Obstructive Pulmonary Disease, and Parkinson Disease). This work has resulted in the development and dissemination of a novel, evidenced based and standardized method for the analysis of videofluoroscopic swallowing studies (VFSS) known as the ASPEKT Method (Analysis of Swallowing Physiology: Events, Kinematics and Timing). Using this method, we have determined and published the first comprehensive set of normative reference values for swallowing physiology in a sex-balanced sample of healthy adults up to the age of 60 ([name], Peladeau-Pigeon et al., 2019; [name] Swallowing Lab, 2019) across all liquid consistencies of the International Dysphagia Diet Standardisation Initiative

framework (Cichero et al., 2017; Cichero et al., 2017). Importantly, this work has afforded clinicians and researchers the ability to understand mechanisms of swallowing impairment in their patients, by providing a normative reference framework to index and identify specific measures of swallowing that fall outside the range of normal variation. We have recently extended this work by completing the analysis of a dataset collected in a sex-balanced sample of healthy older adults (> age 60) (in progress), which now enables us to account for age related changes when using reference data to identify swallowing pathophysiology in older patients.

Systematic methods for analyzing these data have enabled us to identify abnormalities in swallowing that most commonly explain penetration-aspiration and pharyngeal residue. In the proposed study, we will use the ASPEKT Method to identify pathophysiological mechanisms of impaired swallowing in PrC-19. Findings from the proposed study will provide foundational evidence for treatment recommendations in PrC-19 with dysphagia.

In healthy individuals, the swallow is usually positioned partway through an outward breath, such that the respiratory pause associated with swallowing is bracketed on either side by expiration (Brodsky et al., 2010; Martin-Harris, 2008; Martin-Harris et al., 2005; Butler et al, 2007). This positioning of swallowing in the respiratory cycle is considered optimal for airway protection, so that any remaining material in the laryngeal vestibule may be expelled by exhalation immediately after the swallow. Post-swallow inspiration has been observed as an abnormal respiratory-swallow coordination pattern in some clinical populations and is thought to represent a risk for aspiration of material into the airway (Brodsky et al, 2018; Brodsky et al., 2010; Butler et al, 2007; Martin-Harris et al., 2017). Incorporating measurements of respiratory-swallow phasing into clinical swallowing assessments has the potential to identify individuals at heightened risk of aspiration.

Historically, the combined measurement of breathing and swallowing has been a research activity using either nasal cannula methods or the measurement of chest wall movements via respiratory inductance plethysmography. There is a need for new, portable cost-effective methods that can reliably and validly measure respiratory-swallow dynamics during clinical assessment. As an exploratory objective, we will address this need with timely implementation of a novel digital stethoscope technology. Co-investigators [name] and [name] have developed a novel digital stethoscope (the “E-Steth”) for use in telehealth community monitoring of cardio-respiratory function in PrSC-19. This innovative device uses a microphone mounted inside a stethoscope head to record physiological sounds into the Voice-Memo application on a smart phone. The recording can easily be sent to a clinician, who can run diagnostic signal processing algorithms. In this study, we will adapt the E-Steth technology to identify abnormalities in respiratory-swallow coordination, in the form of inspiratory airflow immediately after the swallow. Automatic signal processing algorithms previously validated for the measurement of airflow in sleep (Montazeri et al., under review) can be used to classify post-swallow airflow direction as expiratory (typical) or inspiratory (abnormal).

3.2 Objectives

Our objective is to understand the nature of swallowing impairment in PrC19, based on the following outcome measures:

Primary Outcomes:

- Frequency of boluses (per consistency) on which the participant displays unsafe swallows defined as scores of 3 or higher on the Penetration-Aspiration Scale (Rosenbek et al., 1996)
- Frequency of boluses (per consistency) on which the participant displays inefficient swallows defined as swallows with pharyngeal residue measured to fill 1% or more of an anatomical reference scalar $[(C2-4)^2]$ on a lateral view x-ray ([name], 2020).

Secondary Outcomes:

- Frequency of boluses (per consistency) on which the participant displays time-to-laryngeal vestibule-closure more than 1 standard deviation above the healthy reference mean ([name] et al., 2019)
- Binary classification of a single pixel-based measure of pharyngeal area at rest, traced from a lateral view x-ray, and classified as below or above 1 standard deviation from the healthy reference mean ([name] et al., 2019)
- Frequency of boluses (per consistency) on which the participant displays pharyngeal area above the 75th percentile healthy reference value on the frame of maximum constriction ([name] et al., 2019)
- Frequency of boluses (per consistency) on which the participant displays multiple swallows, above the 75th percentile healthy reference value ([name] et al., 2019)

Exploratory Outcomes:

- Frequency of boluses (per consistency) on which post-swallow inspiration is seen immediately following the swallow.
- Maximum value across 3 repetitions of a maximum tongue-palate press using the Iowa Oral Performance Instrument in an anterior position.
- Range of diet textures included in the participant's diet, measured using the International Dysphagia Diet Standardisation Initiative Functional Diet Scale
- Total and individual question scores on the Sydney Swallow Questionnaire
- Reported dyspnea using the Modified Medical Research Council Dyspnea Scale
- Maximum peak voluntary cough flow across 3 repeated coughs through a peak-flow meter
- Patient report of any changes (Yes/No) they have experienced in taste or smell associated with their COVID-19 infection

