3.3 Hypothesis

Our current expectations are that PrC-19 will show differences in swallowing function and physiology compared to age- and sex-matched reference values ([name], 2019), as listed in the following table:

Parameter	Prediction in PrC-19 (vs age-matched healthy reference values)
Penetration-Aspiration	Higher frequency and more likely to be silent
Time-to-Laryngeal-Vestibule-Closure (LVC)	Later closure due to priority of respiration
LVC duration	Shorter due to underlying respiratory challenges
Pharyngeal Area at Rest	Larger due to muscle weakness and atrophy. Note: reference values show significant sex difference with larger area in males.
Pharyngeal Area at Maximum Constriction	Larger (i.e. poor constriction) due to muscle weakness and atrophy
Residue	Greater due to poor constriction
# of swallows per bolus	Higher due to poor bolus clearance

We expect PrC-19 patient to report swallowing-related burden. We hypothesize that post-swallow inspiration (a sign of respiratory-swallow discoordination) will be seen more commonly in PrC-19 compared to healthy reference data (Valenzano et al, 2020), and will be particularly common in those who report dyspnea.

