7.0 Statistics

We will use the ASPEKT Method ([name] et al., 2019) to analyze available recordings of thin liquid, mildly thick liquid and extremely thick liquid swallows, and compare values to age matched reference data ([name] Swallowing Lab, 2019). Our goal is to develop an understanding of the prevalence of

abnormal values in PrC-19 taking comorbidities and other related factors into consideration. These potential covariate moderators include demographic factors (sex, age, gender, race, ethnicity), pre-existing or co-existing medical diagnoses, history of the COVID-19 hospitalization including details of any ventilator support required, medical history since discharge (including any occurrences of respiratory infection), dyspnea, changes in taste and/or smell associated with the COVID-19 infection, bulbar muscle strength, cough strength, and abnormal respiratory-swallow coordination. Additionally, the person's ability to tolerate the full range of diet textures and their swallowing-related quality of life may be affected by COVID-19 related swallowing difficulties.

Assuming 100 participants and 3 boluses per consistency, this will result in a dataset of 300 boluses per consistency. Our previous research suggests that swallowing can differ across repeated boluses of the same consistency within an individual. It is, therefore, reasonable to calculate statistical power at the bolus level. A power calculation in Study Size software suggests that a sample of 138 boluses for a given consistency will be needed to detect frequencies of abnormal values higher than those seen in the healthy reference sample with odds ratios ≥ 2.00 with 80% power. Therefore, the targeted sample size should be sufficient both to detect increased frequencies of abnormal values and to allow the bivariate exploration of the impact of single covariate moderators on abnormal value frequency. We will not have sufficient data to create a multivariate model exploring the relative impact of different moderators; however the findings from this analysis will be sufficient to inform future studies in larger cohorts.

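### Pharyngeal area at rest has one value per participant, so the bolus-level power in section 7.0 does not cover it, and its two-way class is unclear in direction and loses information

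*Combined protocol and SAP*

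**What the plan says.** Section 3.2 (Secondary Outcomes) defines the outcome as "Binary classification of a single pixel-based measure of pharyngeal area at rest, traced from a lateral view x-ray", and then "classified as below or above 1 standard deviation from the healthy reference mean". The Protocol Summary words it slightly differently: "Pixel-based measurement of pharyngeal area at rest from a single a lateral view x-ray image, and classified as below or above 1" SD. It names the measurement as well as the class and omits the word binary.

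Section 3.3 predicts one direction for this parameter: "Larger due to muscle weakness and atrophy. Note: reference values show significant sex difference with larger area in males". The same section refers to reference values matched on age and sex, whereas section 7.0 mentions matching on age only.

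The other outcomes cut at 1 SD have a stated direction. One is "time-to-laryngeal vestibule-closure more than 1 standard deviation above the healthy reference mean"; the Protocol Summary gives closure duration a cut on the low side.

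Section 7.0 bases the sample size on boluses: "Assuming 100 participants and 3 boluses per consistency, this will result in a dataset of 300 boluses per consistency". It reports that "a sample of 138 boluses for a given consistency will be needed" to detect odds ratios of at least 2.00 with 80% power. It then concludes, with no outcome excepted, that the target is enough to detect raised frequencies of abnormal values.

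**The concern.** The case for counting boluses in section 7.0 is that swallows vary within a person across repeats. That argument cannot apply to an outcome traced from one image per person. The sufficiency statement therefore has no stated basis for resting area, and a non-significant result on it could be wrongly read as coming from an adequately sized comparison.

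The class raises two further issues. It can be read as a single upper cut, or as flagging values beyond 1 SD on either side, so two analysts could report different prevalences from the same data. On either reading, a measured number becomes a yes/no, and the plan describes no test that uses the number itself.

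**Working it through.** **Inputs from the documents.** 100 participants; one value each; odds ratio 2.00; 80% power; 138 boluses per consistency (sections 3.2 and 7.0).

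**Not given, so assumed.** Two-sided alpha 0.05; area normal in the reference population with the same SD in participants; reference either a fixed known value or a sample of 100. The documents do not give alpha, sidedness, reference abnormal rate, reference sample size or the test.

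**The plan's own figure.** 138 cannot be reproduced from the stated inputs alone. With alpha 0.05 and odds ratio 2, several settings come close:
- a two-sided two-sample test at a reference rate of 0.317 (139 per group) or 0.50 (137 per group)
- a one-sided two-sample test at 0.20 (135 per group)
- a one-sample test at a rate of about 0.09 (two-sided) or 0.07 (one-sided)

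So 138 is plausible, but it is not tied to any rate that applies to resting area.

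**Effect size on the SD scale.** Under normality, P(Z > 1) = 0.1587, with odds 0.1587/0.8413 = 0.1886. Doubled, this is 0.3772, a proportion of 0.3772/1.3772 = 0.2739. Solving P(Z > 1 − d) = 0.2739 gives d = 1 − 0.601 = 0.399, about 0.40 SD.

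**Upper cut, fixed reference.** Power = Φ{[√n(p1 − p0) − 1.96√(p0q0)] / √(p1q1)} = Φ{[10 × 0.1152 − 1.96 × 0.3654] / 0.4459} = Φ(0.98) = 84%. The n for 80% power is [(1.96 × 0.3654 + 0.8416 × 0.4459) / 0.1152]², which rounds up to 90.

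**Upper cut, 100 reference subjects.** With pooled rate 0.2163, power = Φ{[10 × 0.1152 − 1.96 × √(2 × 0.2163 × 0.7837)] / √(0.1335 + 0.1989)} = Φ(0.02) = 51%. The n for 80% power is 200 per group.

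**Both sides pooled.** The share beyond 1 SD moves from 0.3173 to 0.2739 + 0.0809 = 0.3548. The odds ratio is 0.5499/0.4648 = 1.18, because losses in the lower tail offset gains in the upper. The same formulas give Φ(−1.12) = 13% and Φ(−1.40) = 8%. About 1,231 participants would be needed for 80% power against a fixed reference.

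**Continuous value.** One-sample t-test: noncentrality 0.399 × √100 = 3.99, power 98%, n for 80% power about 52. Two-sample t-test: noncentrality 0.399 × √50 = 2.82, power 80%.

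**Power at n = 100 over a range of shifts (fixed reference / 100 reference subjects):**

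| Shift (SD) | Continuous | Upper cut | Both sides pooled |
|---|---|---|---|
| 0.2 | 51% / 29% | 33% / 16% | 4% / 4% |
| 0.3 | 84% / 56% | 61% / 31% | 7% / 5% |
| 0.40 | 98% / 80% | 84% / 51% | 13% / 8% |
| 0.5 | 99.9% / 94% | 96% / 71% | 25% / 14% |

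**Information kept by the upper cut.** Asymptotic relative efficiency = φ(1)² / [Φ(1)(1 − Φ(1))] = 0.0586 / 0.1335 = 0.44, so about 56% is lost.

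**Smallest odds ratio detectable with 80% power, upper cut, n = 100.** 1.94 against a fixed reference; 2.58 against 100 reference subjects.

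**The case against.** The strongest reply has four parts.

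First, the upper-cut reading is the natural one. Two classes called below and above suggest one threshold; pooling the tails would give within and outside, terms the definition does not use. Section 3.3 expects only a larger area, and the companion 1-SD outcomes each run in one direction. This stands. A reader might infer that the classification discards most of the outcome's power, but that is true only if the tails are pooled. Under an upper cut against a fixed reference, power is 84%, above the plan's 80% target.

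Second, 138 counts boluses within a consistency and rests on an undisclosed reference rate. A reader might infer from 100 being less than 138 that this outcome is too small. The documents do not support that: depending on the reference, the requirement is 90 participants or 200 per group. The calculation fails to cover the outcome; it does not show a shortfall.

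Third, the Protocol Summary names the measurement itself, and section 7.0 speaks generally of comparing values with reference data. So the number is not shown to be thrown away. Even so, neither place describes a test of it.

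Fourth, section 7.0 aims at the prevalence of abnormal values, and a test of means answers a different question. This is a good reason to keep the prevalence, but not a reason to leave the continuous value untested.

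**Conclusion.** The concern holds in a limited form. Section 7.0 offers no support for its sufficiency statement as applied to resting area, which supplies at most 100 values. The class needs a stated direction. If the intended class is an upper cut, using it alone gives up about 56% of the information: at a 0.40 SD shift, power goes from 98% to 84% against a fixed reference, or from 80% to 51% against 100 reference subjects. The collapse to 13% or 8% belongs only to the less likely pooled reading.

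These figures rest on assumed normality, equal SDs, two-sided alpha 0.05 and a reference that is either known without error or equal in size. The actual reference size is not in the documents, so whether power is adequate remains open. This is a secondary outcome in an observational study; the point affects how its result can be read, not the primary outcomes.

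**What to change.** In section 3.2 and the Protocol Summary, define the abnormal flag as an area more than 1 SD above the age- and sex-matched healthy mean, and report its prevalence, which serves the aim in section 7.0. Add a test of the continuous area, expressed as an age- and sex-standardised z-score, against the reference. Standardising on sex alone would drop the age matching that sections 3.3 and 7.0 call for.

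In section 7.0, limit the sufficiency statement to outcomes measured per bolus. Add a participant-level power statement for n = 100 that gives alpha, sidedness, the reference rate, the reference sample size, and whether the reference is treated as fixed or as a sample.

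The cost is wording and one extra analysis; the tracing already yields a number, so no new data are needed. The added test relies on an approximately normal measure, which should be checked. The power statement for this outcome may look less favourable than the present blanket claim.
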